#### **5.7. Ophthalmological examination**

ophthalmological examination results are given in a list.

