mg (6 subjects) dose groups, the ORR was 66.7% and the DCR was 100.0%; in the 220 mg dose group (6 subjects), the ORR was 50.0% and the DCR was 83.3%; and in the 260 mg dose group, the treatment response assessment was completed in only 3 subjects, with the DCR of 33.3%.

The enrollment of T790M mutation-positive population for the phase I extension study of HS-10296 has been completed, with a total of 91 subjects enrolled in the 55 mg (30 subjects), 110 mg (30 subjects), and 220 mg (31 subjects) dose groups. In terms of safety, common adverse events (AEs) were rash, asthenia, hazy vision, leukopenia, digestive tract symptoms (e.g., constipation, diarrhoea, nausea), blood creatine kinase increased, and blood alanine aminotransferase increased, with mild symptoms or no clinical symptoms, and most AEs could resolve spontaneously. There were no drug-related serious adverse events (SAEs) in the 55 mg and 110 mg dose groups. In the 220 mg dose group, the incidence and severity of AEs were significantly increased. In terms of treatment response, the overall ORR was 50.0% and the DCR was 92.1% in the periodic evaluable patients (n = 76). Of these, the ORR was 53.3% and the DCR was 83.3% in the 55 mg (30 subjects) dose group; the ORR was 46.7% and the DCR was 96.7% in the 110 mg (30 subjects) dose group; and the ORR was 50.0% and the DCR was 100.0% in the 220 mg (16 subjects) dose group.

The data from the 55 mg and 110 mg dose groups in the dose escalation and expansion stages were pooled and analyzed: in the phase I clinical trial of HS-10296 as the second-line therapy in the patients with advanced NSCLC, 36 T790M mutation-positive patients were enrolled in the 55 mg and 110 mg dose groups, respectively, and the last patient was followed up for up to 3 months after enrollment. At least 2 response evaluations had been performed for all the cases. Currently, there were no unexpected safety concerns in either dose group. In terms of treatment response observed in patients with T790M mutation, the overall ORR was 52.1%, of which, 55.6% were in the 55 mg dose group and 50.0% in the 110 mg dose group; the overall DCR was 92.6%, with 86.1% in the 55 mg dose group and 97.2% in the 110 mg dose group.

Taken together these preclinical and clinical data, the objective of this study was to evaluate the efficacy and safety of HS-10296 compared with gefitinib as the first-line therapy in subjects with advanced EGFR⁺ NSCLC who have not received any systemic therapy.

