5.2.2 Safety Endpoints

Occurrence of adverse events; occurrence of serious adverse events; proportion of patients withdrawn from the study due to adverse events; laboratory test result changes (blood chemistry, hematology, and urinalysis); changes in vital signs, physical examination, body weight, 12-lead electrocardiogram (ECG), left ventricular ejection fraction (LVEF), ECOG performance status (PS) score, and ophthalmic examination.

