12.3 Statistical Analytical Methods

12.3.1 Definitions of Statistical Analysis Sets

- Full Analysis Set (FAS)**

The full analysis set is defined as all randomized patients who have received at least one dose of the study drug, and inter-group comparisons will be based on the randomization results, regardless of whether actually receiving the study treatment assigned to this group.

- Per Protocol Set (PPS)**

The per protocol set is defined as all patients who are complied with the protocol, have good

protocol compliance, and have no major protocol violations. The PPS is a subset of the FAS. Baseline and demographic characteristics will be analyzed using the FAS, and efficacy evaluation will be performed on both the FAS and the PPS, with results mainly based on the FAS.

- **Safety Set (SS)**

The safety set is defined as all randomized patients who have received at least one dose of the study drug, but inter-group comparisons will be summarized by the group in which they actually receive treatment, e.g., for patients who are inappropriately administered: they are randomized to receive treatment A, while they actually receive treatment B, and the safety data should be calculated and included in the group B. Safety evaluations will be analyzed based on the SS.

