12.3.3.4 Ophthalmological Examination

Qualitative data from ophthalmic examinations, such as normal or not and with or without clinical significance, will be tabulated to describe the changes from baseline to each post-dose follow-up visit.

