### 1.3.3. Safety Evaluation Indicators

The safety endpoints include:

- 1) Adverse events and serious adverse events
- 2) Laboratory testing
  - Clinical blood biochemistry: Albumin, ALT, AST, alkaline phosphatase, bilirubin, total bilirubin, calcium, total blood calcium, creatinine, creatine kinase, glucose, LDH, HbA1C, magnesium, potassium, sodium, urea nitrogen or urea (pick one of two)
  - Hematology: Hemoglobin, white blood cells, hematocrit, red blood cell count (RBC), absolute white blood cell count (neutrophils, lymphocytes, monocytes, basophils, eosinophils), platelet count, reticulocyte count
  - Urinalysis: Glucose, urine protein, blood in urine
- 3) Vital signs: Pulse, sitting systolic and diastolic blood pressure, respiratory rate, and body temperature.
- 4) Physical examination: Including general condition, skin and mucous membranes, lymph nodes, head, neck, chest, abdomen, spine, and limbs or other examinations.
- 5) Weight
- 6) 12-lead electrocardiogram (ECG): Heart rate (beats/minute), QRS duration (ms), PR interval (ms), RR interval (ms), QT and QTcF intervals (ms), and clinical classification of normal/abnormal ECG.
- 7) ECOG Performance Status Score
- 8) LVEF Measured With Echocardiography or MUGA
- 9) Changes of ophthalmological examination

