## **6. Modifications to the Analysis Plan**

In accordance with the NMPA anti-tumor drug clinical trial endpoint technical guidelines, the definition of overall survival is modified from “the time between the first medication date and the date of patient death from any cause” to “the time from the start of randomization to death from any cause.” This modification will not affect the primary efficacy endpoint results.

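### The SAP plans only a listing for change in ophthalmological examination, a stated safety endpoint that the protocol says will be tabulated from baseline, and does not declare the departure

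*SAP*

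**What the plan says.** Protocol 5.2.2 closes its list of safety endpoints, which includes a series of changes, with "ECOG performance status (PS) score, and ophthalmic examination". SAP 1.3.3, item 9, names "Changes of ophthalmological examination". Protocol 12.3.3.4 gives the analysis: ophthalmic data classed as normal or not, and "with or without clinical significance, will be tabulated to describe the changes from baseline to each post-dose follow-up visit".

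The SAP does something else. Section 5.7 consists of one statement, that "ophthalmological examination results are given in a list". Section 3.7 likewise puts the eye results in a list, beside surgical and allergy history. In section 7 the only ophthalmic output is List 16.2.8.8.

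SAP section 6, which records departures from the protocol, holds a single item: "the definition of overall survival is modified from" first dose to randomization as the starting point. The SAP's revision history mentions the eye only to say that the listing was widened from clinically significant abnormal results to all results.

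**The concern.** The eye is a known site of toxicity for this drug. Protocol 4.2.3 names it, with skin and gastrointestinal tract, as a main site of toxicity in rats and dogs. Protocol 4.2.4 reports from the phase I expansion cohorts that "common adverse events (AEs) were rash, asthenia, hazy vision, leukopenia" and others, and protocol 4.3.1 adds cataract and dry eye from completed trials. Every patient has a full baseline examination (best corrected visual acuity, intraocular pressure, fundus, slit lamp), yet no planned table uses it.

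Comparing safety between the two drugs is a secondary objective. A patient-level listing does not summarize change by treatment group, so the report would carry no such summary for this endpoint unless someone built one after seeing the data. The departure is also undeclared, so a reader of SAP section 6 would conclude that the protocol's eye analysis was kept.

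**Working it through.** No figure in the plan bears on this, so the check compares the texts.

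**1. Is there an eye table anywhere in the SAP?** The safety tables in SAP section 7 are:

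| Block | Content | Tables |
|---|---|---|
| 14.3.1 | Adverse events | 27 |
| 14.3.2 | Laboratory tests | 11 |
| 14.3.3 | ECG | 5 |
| 14.3.4 | Vital signs, ECOG | 2 |
| 14.3.5 | LVEF | 2 |
| 14.3.6 | Physical examination | 2 |

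Total: 27 + 11 + 5 + 2 + 2 + 2 = 49. None is devoted to the ophthalmological examination, against one listing (16.2.8.8). The terse wording of 5.7 is not made good elsewhere. SAP 5.4 also promises only lists for physical examination, but section 7 adds Tables 14.3.6.1 and 14.3.6.2; nothing similar is added for the eye. SAP 2.2.6 does not name eye examinations among the data assigned to analysis visits.

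**2. Does the protocol's wording mean a summary table?** Protocol 12.2 does use the word loosely, for adverse events before the first dose, where a listing is probably meant. But protocol 12.3.3.2 has a nearly identical sentence for qualitative laboratory data, and the SAP turns that into cross tables (5.2; Tables 14.3.2.6 to 14.3.2.8). The consistent reading of 12.3.3.4 is a cross table too.

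**3. By treatment group?** Section 12.3.3.4 does not say so. It follows from protocol 12.3.1, where for the safety set "inter-group comparisons will be summarized by the group in which they actually receive treatment", and from the objective of comparing safety.

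**4. Is the departure declared?** SAP section 6 declares one change, on overall survival, and none on ophthalmology.

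**5. What do the other outputs already cover?** Protocol 10.1.13 requires clinically significant eye findings and symptoms to be reported as adverse events. SAP 5.1 summarizes these by treatment group, system organ class and preferred term, and again by grade, relatedness and action taken. Those tables do not show baseline status, shifts from normal to abnormal without clinical significance, or how many patients were examined.

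**6. When are eyes examined after baseline?** Only as clinically indicated (protocol 9.1.2.2 and 10.1.13), with the items chosen case by case. A table by visit would therefore be sparse and selective.

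**The case against.** The strongest reply is that adverse event tables already do the work. Post-baseline examinations are triggered mainly by symptoms, so most patients examined should already appear in those tables through the symptom. The clinical significance category in any new table rests on the same site judgement. This largely stands, and it rules out a stronger conclusion that a reader might draw, namely that the endpoint would have no result by treatment group at all.

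A reader might also infer that the number examined is lost. It is not: the listing now covers all results, so the count can be made from it. It is inconvenient to obtain, and in neither document is it part of the endpoint as worded.

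The physical examination may overlap as well, since protocol 10.1.6 includes the eyes among the systems examined at baseline and Tables 14.3.6.1 and 14.3.6.2 give before-and-after results. This carries less weight: it is not a slit-lamp or fundus examination, and SAP 1.3.3 does not list eyes separately under physical examination.

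Finally, sparse, unscheduled examinations are a plausible reason for choosing a listing. They justify adapting the protocol's layout, but the choice still needs to be declared.

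**Conclusion.** The mismatch is real and minor. The protocol specifies a tabulation of change from baseline, the SAP replaces it with a listing, and section 6 is silent. The loss is confined to the summary by treatment group of change in eye examination, including abnormalities judged not clinically significant, and to a ready count of patients examined. The primary endpoint is unaffected.

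The number of patients concerned cannot be sized. An assumed examination rate of 5% to 20% in 410 / 2 = 205 patients per arm would give 205 × 0.05 ≈ 10 to 205 × 0.20 = 41, but nothing in the documents supports that range and the conclusion does not use it.

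Two readings underlie the conclusion: that the tabulation means a summary table, supported by how the matching laboratory sentence was carried out, and that it is by treatment group, inferred from the safety set definition. The SAP states that it is based on protocol version 03; the version of the protocol supplied could not be checked.

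**What to change.** Add to SAP 5.7 and section 7 a descriptive table by treatment received, on the safety set and for the randomized stage only:

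- The number and percentage of patients with at least one post-baseline ophthalmological examination.
- A cross table of baseline category (normal, abnormal not clinically significant, abnormal clinically significant) by worst post-baseline category. Build it separately for visual acuity, intraocular pressure, fundus and slit lamp, and compare only components examined at both times. Without this rule, a partial examination prompted by symptoms would be set against a full baseline. Show percentages both of all treated patients and of those examined.

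Keep List 16.2.8.8. Record in SAP section 6 that worst post-baseline category replaces the protocol's layout by visit, because examinations are done only as clinically indicated. Footnote that the table is descriptive, because examinations are symptom-triggered.

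The cost is SAP wording and a small set of tables from results that protocol 10.1.13 already requires in the eCRF. The physical examination tables could serve as a template. Before committing, check that the eCRF holds the normal/abnormal and significance categories for each component, which the documents do not state. No examination schedule or clinical rule changes. If the team prefers to keep only the listing, the minimum is a sentence in section 6 that declares and justifies it. That would settle the inconsistency but not restore the summary.

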## **6. Modifications to the Analysis Plan**

In accordance with the NMPA anti-tumor drug clinical trial endpoint technical guidelines, the definition of overall survival is modified from “the time between the first medication date and the date of patient death from any cause” to “the time from the start of randomization to death from any cause.” This modification will not affect the primary efficacy endpoint results.

## 7. Statistical Analysis Form

The list of statistical analysis charts follows:

14.1 Subject Information
14.1.1 Distribution of subjects
Table 14.1.1.1 Summary of screening failures-all screened subjects
Table 14.1.1.2 Subject distribution-all randomized subjects
Table 14.1.1.3 Distribution of subjects in each analysis set-all randomized subjects
14.1.2 Protocol Deviations
Table 14.1.2.1 Summary of serious protocol deviations during the randomized, double-blind treatment stage-full analysis set
Table 14.1.2.2 Summary of serious protocol deviations during the randomized, double-blind treatment stage (excluding those caused by the epidemic)-full analysis set
14.1.3 Demographic data and baseline data
Table 14.1.3.1 Summary of subject demographic data and baseline characteristics-full analysis set
Table 14.1.3.2 Summary of subject demographic data and baseline characteristics-per-protocol set
Table 14.1.3.3 Summary of subject baseline disease characteristics-full analysis set
Table 14.1.3.4 Summary of subject baseline disease characteristics-per-protocol set
14.1.4 Past medical history
Table 14.1.4.1 Summary of past medical history-full analysis set
14.1.5 Past concomitant medications
Table 14.1.5.1 Summary of past medications by ATC3 and PT-full analysis set
Table 14.1.5.2 Summary of past medications by ATC1 and ATC3-full analysis set
Table 14.1.5.3 Summary of concomitant medications by ATC3 and PT-full analysis set
Table 14.1.5.4 Summary of concomitant medications by ATC1 and ATC3-full analysis set
14.1.6 Past, concomitant and subsequent anti-tumor therapy
Table 14.1.6.1 Summary of past anti-tumor treatment by treatment category and treatment type-full analysis set
Table 14.1.6.2 Summary of concomitant anti-tumor medications by ATC3 and PT-full analysis set
Table 14.1.6.3 Summary of subsequent anti-tumor treatment by ATC3 and PT-full analysis set
14.1.7 Subject exposure and medication compliance
Table 14.1.7.1 Summary of drug exposure time and compliance-safety set
14.2 Efficacy evaluation
14.2.1 Analysis based on endpoint PFS as evaluated by the investigator (primary event censoring rules)-full analysis set
Table 14.2.1.1 Statistical analysis based on PFS as evaluated by the investigator (primary event censoring rules)-full analysis set
Figure 14.2.1.1 Kaplan-Meier curve based on PFS as evaluated by the investigator (primary event censoring rules)-full analysis set
14.2.2 Analysis based on endpoint PFS as evaluated by the investigator (primary event censoring rules and considering primary drug resistance)-full analysis set
Table 14.2.2.1 Statistical analysis based on PFS as evaluated by the investigator-full analysis set (excluding subjects with primary drug resistance)
Figure 14.2.2.1 Kaplan-Meier curve based on PFS as evaluated by the investigator-full analysis set (excluding subjects with primary drug resistance)
14.2.3 Analysis based on endpoint PFS as evaluated by the investigator (primary event censoring rules)-per-protocol set
Table 14.2.3.1 Statistical analysis based on PFS as evaluated by the investigator (primary event censoring rules) - per-protocol set
Figure 14.2.3.1 Kaplan-Meier curve based on PFS as evaluated by the investigator (primary event censoring rules)-per-protocol set
14.2.4 Analysis based on endpoint PFS as evaluated by the investigator (secondary event censoring rules)-full analysis set
Table 14.2.4.1 Statistical analysis based on PFS as evaluated by the investigator (secondary event censoring rules)-full analysis set
Figure 14.2.4.1 Kaplan-Meier curve based on PFS as evaluated by the investigator (secondary event censoring rules)-full analysis set
14.2.5 Analysis based on endpoint PFS as evaluated by the IRC (primary event censoring rules)-full analysis set
Table 14.2.5.1 Statistical analysis based on PFS as evaluated by the IRC (primary event censoring rules)-full analysis set
Figure 14.2.5.1 Kaplan-Meier curve based on PFS as evaluated by the IRC (primary event censoring rules)-full analysis set
14.2.6 Analysis based on endpoint PFS as evaluated by the investigator (primary event censoring rules and considering the impact of the COVID-19 epidemic)-full analysis set

Table 14.2.6.1 Statistical analysis based on PFS as evaluated by the investigator (primary event censoring rules and considering the impact of the COVID-19 epidemic)-full analysis set
Figure 14.2.6.1 Kaplan-Meier curve based on PFS as evaluated by the investigator (primary event censoring rules and considering the impact of the COVID-19 epidemic)-full analysis
14.2.7 Analysis based on endpoint PFS as evaluated by the investigator (primary event censoring rules and considering changes in the assessment cycle)-full analysis set
Table 14.2.7.1 Statistical analysis based on PFS as evaluated by the investigator (primary event censoring rules and considering changes in the assessment cycle)-full analysis set
Figure 14.2.7.1 Kaplan-Meier curve based on PFS as evaluated by the investigator (primary event censoring rules and considering changes in the assessment cycle)-full analysis set
14.2.8 Subgroup analysis based on PFS as evaluated by the investigator (based on the primary event censoring rules)-full analysis set
Figure 14.2.8.1 Forest plot of subgroup analysis based on PFS as evaluated by the investigator (based on the primary event censoring rules)-full analysis set
14.2.9 Subgroup analysis based on PFS as evaluated by the investigator (based on the primary event censoring rules) by EGFR gene mutation type-full analysis set
Figure 14.2.9.1 Kaplan-Meier curve of subgroup analysis based on PFS as evaluated by the investigator (based on the primary event censoring rules) by EGFR gene mutation type-
14.2.9a Subgroup analysis based on PFS as evaluated by the investigator (based on the primary event censoring rules) by EGFR gene mutation type-full analysis set
Figure 14.2.9.1a Kaplan-Meier curve of subgroup analysis based on PFS as evaluated against IRC (based on the primary event censoring rules) by EGFR gene mutation type-full analysis set
14.2.10 Subgroup analysis based on PFS as evaluated by the investigator (based on the primary event censoring rules) by brain metastasis status-full analysis set
Figure 14.2.10.1 Kaplan-Meier curve of subgroup analysis based on PFS as evaluated by the investigator (based on the primary event censoring rules) by brain metastasis status-
14.2.10a Subgroup analysis based on PFS as evaluated by the investigator (based on the primary event censoring rules) by brain metastasis status-full analysis set
Figure 14.2.10.1a Kaplan-Meier curve based on PFS as evaluated by the IRC (primary event censoring rules) by brain metastasis status-full analysis set
14.2.11 Analysis of overall survival-full analysis set
Table 14.2.11.1 Statistical analysis of overall survival-full analysis set
Figure 14.2.11.1 Kaplan-Meier curve of overall survival-full analysis set
14.2.12 Analysis of overall survival-per-protocol set
Table 14.2.12.1 Statistical analysis of overall survival-per-protocol set
Figure 14.2.12.1 Kaplan-Meier curve of overall survival-per-protocol set
14.2.13 Analysis of objective response and disease control-full analysis set
Table 14.2.13.1 Statistical analysis of objective response rate and disease control rate as evaluated by investigator-full analysis set
Table 14.2.13.2 Statistical analysis of duration of response as evaluated by investigator-full analysis set (only including subjects with objective response)
Figure 14.2.13.1 Kaplan-Meier curve based on PFS as evaluated by the investigator-full analysis set
14.2.14 Analysis of depth of response-full analysis set
Table 14.2.14.1 Summary of analysis based on best depth of response as evaluated by the investigator-full analysis set
Table 14.2.14.2 Changes in depth of response as evaluated by the investigator summarized by visit-full analysis set
Figure 14.2.14.1 Waterfall plot based on best depth of response as evaluated by the investigator-full analysis set
14.3 Safety evaluation
14.3.1 Summary of adverse events
Table 14.3.1.1 Summary of all adverse events-safety set
Table 14.3.1.2 Summary of adverse events by system organ class and preferred term-safety set
Table 14.3.1.3 Summary of investigational drug-related adverse events by system organ class and preferred term-safety set
Table 14.3.1.4 Summary of adverse events of CTCAE grade $\geq 3$ by system organ class and preferred term-safety set
Table 14.3.1.5 Summary of investigational drug-related adverse events of CTCAE grade $\geq 3$ by system organ class and preferred term-safety set
Table 14.3.1.6 Summary of serious adverse events by system organ class and preferred term-safety set
Table 14.3.1.7 Summary of investigational drug-related serious adverse events by system organ class and preferred term-safety set

Table 14.3.1.8 Summary of common ( $\geq 10\%$ ) adverse events by system organ class and preferred term-safety set
Table 14.3.1.9 Summary of common ( $\geq 10\%$ ) investigational drug-related adverse events by system organ class and preferred term-safety set
Table 14.3.1.10 Summary of adverse events causing the suspension of medication by system organ class and preferred term-safety set
Table 14.3.1.11 Summary of investigational drug-related adverse events causing the suspension of medication by system organ class and preferred term-safety set
Table 14.3.1.12 Summary of adverse events causing dose reduction by system organ class and preferred term-safety set
Table 14.3.1.13 Summary of investigational drug-related adverse events causing dose reduction by system organ class and preferred term-safety set
Table 14.3.1.14 Summary of adverse events causing permanent discontinuation by system organ class and preferred term-safety set
Table 14.3.1.15 Summary of investigational drug-related adverse events causing permanent discontinuation by system organ class and preferred term-safety set
Table 14.3.1.16 Summary of adverse events causing death by system organ class and preferred term-safety set
Table 14.3.1.17 Summary of investigational drug-related adverse events causing death by system organ class and preferred term-safety set
Table 14.3.1.18 Summary of all adverse events and adverse events of CTCAE grade $\geq 3$ by system organ class and preferred term-safety set
Table 14.3.1.19 Summary of all investigational drug-related adverse events and adverse events of CTCAE grade $\geq 3$ by system organ class and preferred term-safety set
Table 14.3.1.20 Summary of adverse events of CTCAE grade $\geq 3$ and investigational drug-related adverse events of CTCAE grade $\geq 3$ by system organ class and preferred term-safety set
Table 14.3.1.21 Summary of common ( $\geq 10\%$ ) adverse events and adverse events of CTCAE grade $\geq 3$ (incidence rate $\geq 2\%$ ) by system organ class and preferred term-safety set
Table 14.3.1.22 Summary of investigational drug-related common ( $\geq 10\%$ ) adverse events or adverse events of CTCAE $\geq$ grade 3 adverse events (incidence rate $\geq 2\%$ ) by system organ class and PT class-safety set
Table 14.3.1.23 Summary of adverse events by system organ class, preferred term, and drug relation-safety set
Table 14.3.1.24 Summary of adverse events by system organ class, PT and severity (CTCAE grade)-safety set
Table 14.3.1.25 Summary of investigational drug-related adverse events by system organ class, preferred term, and seriousness (CTCAE grade)-safety set
Table 14.3.1.26 Summary of adverse events causing permanent discontinuation and investigational drug-related adverse events causing permanent discontinuation by system organ class and preferred term-safety set
Table 14.3.1.27 Summary of serious adverse events and investigational drug-related serious adverse events by system organ class and preferred term-safety set
